9.6.4 Analysis of additional Secondary outcomes

The incidence rate of STI will be compared between SOC and ALERT- iTAB intervention arms using Fisher's exact test as will the rate of HIV seroconversion between groups (the rate of new HIV is expected to be low). In order to evaluate hypothesis 3c (factors associated with the composite primary endpoint of on therapy and adherence > 90%), multivariable logistic regression models will also be used. A subgroup analysis by treatment arm will be conducted, looking at each arm separately. Descriptive analysis will be performed within each subgroup

to compare adherent versus non-adherent subjects. The models will include the following potential covariates: demographics, ongoing substance use, untreated mental illness, socioeconomic status, HIV risk transmission behaviors, low health/ HIV and system literacy, fear of disclosure and non-English. Further, any covariates (including stratification factors) that are simultaneously unbalanced at baseline (univariate $p < 0.10$) and associated with the outcome (univariate $p < 0.15$) will be included in the model as observed confounders. Sub-group analyses based on race/ ethnicity, gender, primary language, socioeconomic status by randomization arm will also be conducted. Secondary endpoints for adherence will be analyzed analogously to the primary endpoint.

- 9.6.5 Safety and tolerability of daily TDF/FTC given for PrEP including discontinuation for any adverse event, serious adverse events and adverse events (grade 2 or higher) will be compared between study arms. Descriptive statistics will be used to characterize safety events. Fisher's exact test will be used to compare discontinuation rates due to safety and incidence rates of adverse events and serious adverse events. The time to TDF/ FTC discontinuation for adverse events will be compared between groups using the log-rank test and plotted using Kaplan-Meier curves. Similar analysis will be done for the time to discontinuation for any reason (including drop-out or subject electing to stop PrEP due to lack of perceived risk for HIV).

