BIostatISTICS
RESEARCH CENTER

CCTG 595

**A Multicenter, Randomized Study of Text Messaging to Improve
Adherence to PrEP in Risky MSM**

Statistical Analysis Plan

March 18, 2016

Investigators: [name] & [name]

Statistician: [name], MS

CCTG Biostatistics Core Director: [name]

Contents

1 Introduction	3
2 Study Design	3
3 Study Objectives	4
3.1 Primary Objective	4
3.2 Secondary Objectives	4
4 Subject Disposition	5
4.1 Participant Flow Summary	5
4.2 Evaluation of Premature Discontinuation from Study	5
5 Evaluation of Demographics and Baseline Characteristics	6
6 Evaluation of Primary Objective	7
7 Evaluation of Secondary Objectives	9
7.1 Secondary Objective 1	9
7.2 Secondary Objective 2	9
7.3 Secondary Objective 3	9
7.4 Secondary Objective 4	9
8 Evaluation of Safety Measures	10
9 Software	11

1 Introduction

This document describes the statistical analysis plan (SAP) for the CCTG595 clinical trial.

2 Study Design

CCTG595 is a controlled, open-label, two-arm, randomized (1:1) clinical demonstration project to determine if the use of a text message based adherence intervention (iTAB) improves retention and adherence to PrEP compared to standard of care (SoC) PrEP delivery.

The study is expected to enroll a total of 400 subjects. Eligible subjects will include HIV-uninfected men who have sex with men (MSM) and male to female (M to F) transgender individuals who have sex with men at least 17 years of age and who have a recent history of high risk transmission behavior. All subjects will start PrEP with TDF+FTC fixed dose combination given once daily. Subjects will be randomized 1:1 to either the iTAB text messaging adherence reminder intervention with SoC or the SoC alone arm. The randomization will be stratified by clinic site. Subjects placed into the iTAB intervention arm will receive a personalized, automated texting system to maintain adherence and retention. Both groups will receive access to PrEP in accordance with standardized comprehensive methods of prescribing, risk reduction counseling, adherence counseling, and clinical assessments that include safety monitoring, as well as HIV and STD screening. The study will continue for 48 weeks after randomization of the last participant (up to about 2.5 years).

3 Study Objectives

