4.2 Evaluation of Premature Discontinuation from Study

Proportions of subjects prematurely discontinued the study will be compared between the study arms using Fisher's exact test. The numerator will be the number of subjects who marked other than 'complete the study' as the primary reason in the Termination form. The denominator will be the number of subjects who were randomized.

Time to premature discontinuation will be summarized overall, and by study arm using the method of Kaplan and Meier. The cumulative probability of premature discontinuation will be estimated overall and by arm, with 95% confidence interval. Log-rank test will compare time to premature discontinuation between randomized arms.

The survival indicator will be defined (1=early discontinued the study; 0=completed the study). The event time and censoring time will be defined from the baseline date to the termination date indicated in the Termination form.

5 Evaluation of Demographics and Baseline Characteristics

Tables will summarize the study population at baseline, overall and by study arm. Descriptive statistics will be presented as N, mean, standard deviation, minimum, 25th Q, median, 75th Q, maximum for continuous variables; frequency tables (row, column percentages) will be used for categorical variables. Statistical comparisons will be performed between randomized arms using Wilcoxon Rank Sum Test (for continuous variables) or Fisher's exact test (for categorical variables). The following variables will be examined at baseline:

- Age
- Race/Ethnicity (White, Black, Hispanic, Other)
- Education
- Household average monthly income
- Inclusion criteria
- STI status
- Language (English vs Other)
- Substance use (SCID screen)
 - Any drug use reported other than alcohol and marijuana
 - Meth use
- AUDIT score
- DAST score
- Sexual Compulsivity Score (SCS)
- HIV literacy score

6 Evaluation of Primary Objective

The primary objective of the study is to compare the adherence to PrEP during the 48-week study period between the iTAB intervention group and the SoC group.

The primary analysis will be conducted on the modified intent-to-treat (mITT) population (i.e. randomized subjects who started PrEP).

Primary Adherence Endpoint

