Descriptive analysis will look at self-reported adherence, FTC adherence and TFV-DP adherence measures by visit. Continuous outcome will be summarized with N, min, Q1, median, Q3, and max, by study arm and overall. Binary endpoint will be summarized with frequency tables, by study arm and overall. Wilcoxon rank sum test will be used for comparison for continuous outcome; Fisher's exact test will be used for binary outcome.

Statistical Inference

A logistic regression model will be performed to compare the adherence over 48 weeks between the two groups. The model will include baseline factors (refer to the baseline variable list) as covariates if they are found unbalanced between the study arms (with $p < 0.1$) and also univariately associated with the outcome ($p < 0.15$). Interactions between each of the covariates and study arm will also be assessed individually. Significant interactions ($p < 0.05$) will be included in the final model.

7 Evaluation of Secondary Objectives

7.1 Secondary Objective 1

To determine factors associated with poor adherence/lost to PrEP in study participants. Factors will include demographics, ongoing substance use, untreated mental illness, socioeconomic status, low health/HIV and system literacy, fear of disclosure and non-English language.

This objective will be assessed along with the primary objective analysis. The final primary multivariable model will be able to answer this question.

7.2 Secondary Objective 2

To determine the rate of HIV seroconversion in PrEP users and compare the iTAB to SoC arms for number of new infections as a proportion at 48 weeks and end of the study.

Number and proportion of subjects with HIV-seroconversion at 48 weeks will be summarized by study arm and overall. Fisher's exact test will be used for comparison. Same analysis will also look at the rate of seroconversion during the whole study period.

7.3 Secondary Objective 3

To measure acquisition of other sexually transmitted infections (STIs); the proportion of subjects with any new STI at any site will be compared between the iTAB to SoC arms at 48 weeks and end of the study.

Any new STI will be defined as positive results from Gonorrhea (GC) or Chlamydia (CT) at any site or positive syphilis RPR result with titer $>1:4$ based on the STI form collected after baseline visit.

Sensitivity analysis will also be performed looking at STI by testing as well as self-reported STI (outside diagnosis) based on the clinical assessment form.

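### SAP 7.1 answers Secondary Objective 1 with a model that a risk factor can enter only if it is imbalanced between arms by chance; the same model also omits site, at little cost to the primary test

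*SAP*

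**What the plan says.** SAP 2 states: "The randomization will be stratified by clinic site". SAP 5 gives a list headed "The following variables will be examined at baseline", with 13 entries if the two substance-use sub-items are counted. Site is not on it, and no entry measures mental illness or fear of disclosure.

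SAP 6, Statistical Inference, compares the arms by logistic regression. Factors from that list enter "as covariates if they are found unbalanced between the study arms" at p<0.1, provided they are also associated with the outcome at p<0.15. It continues: "Interactions between each of the covariates and study arm will also be assessed individually". Interactions with p<0.05 stay in the final model. Under Descriptive Analysis, the SAP says "Fisher's exact test will be used for binary outcome".

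SAP 7.1 restates Secondary Objective 1, including untreated mental illness and fear of disclosure among its factors, and says of the analysis: "The final primary multivariable model will be able to answer this question".

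Protocol 9.6.4 plans something different for this objective: "The models will include the following potential covariates: demographics, ongoing substance use, untreated mental illness, socioeconomic status", and its list goes on to fear of disclosure. It then adds as confounders "any covariates (including stratification factors) that are simultaneously unbalanced at baseline" and associated with the outcome. Protocol 9.0 says the SAP prevails where the two differ.

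**The concern.** The entry rule was written to pick up confounders of the arm comparison. It does not ask which factors predict adherence. A strong predictor that is balanced between arms, which is what randomisation normally produces, is left out. A model built this way cannot serve an objective about risk factors, and Objective 1 would be reported from whichever factors happened to be imbalanced.

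For the primary comparison, the model ignores the factor on which randomisation was stratified, and the SAP does not say which number is the overall iTAB effect if an interaction is retained.

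**Working it through.** **1. The plan's own figure.** Protocol 9.4 states 94% power (30% vs 15%) and 84% power (30% vs 17%) with 200 per arm and two-sided alpha 0.05. A continuity-corrected normal approximation gives 93.8% and 84.1%, and exact Fisher power is 94.0% and 84.5%, so both figures reproduce. They concern the self-report composite, not the TFV-DP endpoint of SAP 6. The documents give no expected TFV-DP adherence, site rates, covariate effects or block size, so those are assumed below.

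**2. Chance that a factor enters.** With no arm effect the two screens are roughly independent:

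P(enters) ≈ P(imbalance p<0.1) × P(association p<0.15).

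Randomisation fixes the first term near 0.10 whatever the factor does to adherence. The ceiling is therefore about 0.10 × 1 = 10%. An unrelated factor enters with probability 0.10 × 0.15 = 1.5%. Simulation with a binary factor at 50% prevalence, 400 subjects, chi-square screens, a modest arm effect (log odds ratio 0.4) and 10,000 trials per row gives:

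| Odds ratio | Imbalanced | Associated | Enters |
|---|---|---|---|
| 1.5 | 9.7% | 67.1% | 6.6% |
| 2.0 | 9.4% | 95.2% | 9.1% |
| 2.5 | 10.3% | 99.4% | 10.2% |
| 3.5 | 10.3% | 100.0% | 10.3% |

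With the 13 SAP variables, assumed independent distributions and odds ratios of 1.5 or 2.0 per SD, each true predictor enters in 8.4-9.9% of trials.

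**3. Chance that no factor enters.** If none of the 13 is prognostic: 0.985^13 = 82%. If six are strong: 0.90^6 × 0.985^7 = 0.531 × 0.900 = 48%. Simulation (15 settings, 6,000 null trials each) agrees: no factor enters in 50-84% of trials, and on average 0.17-0.67 of the 13 do.

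**4. Named factors against available variables.** SAP 3.2 names untreated mental illness and fear of disclosure, and neither has a variable on the SAP 5 list. Protocol 6.1 (schedule footnotes) and Appendix II show that the PHQ9 and a stigma and disclosure scale are collected at baseline.

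**5. Omitting site.** Settings: 200 per arm, 3 or 4 sites, arms balanced within site, mean adherence 50%, 70% or 80%, effect set for about 80% power without site, 60,000 trials per setting.

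| Site spread | Type I without site | Type I with site | Power lost |
|---|---|---|---|
| 10 points | 4.7-5.2% | 4.9-5.2% | 0-0.3 point |
| 20 points | 4.5-4.9% | 4.7-5.1% | 0.1-1.0 point |
| 35 points | 3.9-4.5% | 5.0-5.3% | 1.3-2.7 points |

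Example, four equal sites at 60-80%: type I error 4.64% vs 5.07%, power 79.7% vs 80.4%.

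**6. Screen and interactions under no arm effect.** In 4,000 trials with 13 binary factors, four of them prognostic (odds ratio 2), the screened model without interactions rejects in 4.7%, against 5.1% unadjusted and 5.2% with prespecified covariates (Monte Carlo SE about 0.3 point). If interactions are tested only for covariates that passed the screen, one enters in 0.7-3.7% of null trials (the 15 settings of step 3).

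**7. Size of a full Objective 1 model.** Thirteen variables with race/ethnicity on 3 df make 15 parameters. Adding two variables for the missing factors, arm, and four sites on 3 df gives 15 + 2 + 1 + 3 = 21, excluding the intercept. At an assumed 85% adherence, 400 × 0.15 = 60 subjects are non-adherent; at 70%, 400 × 0.30 = 120. That is 60/21 = 2.9 to 120/21 = 5.7 events per parameter.

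**The case against.** **Objective 1 is not left with nothing.** Applying the rule produces a univariate outcome association for every listed factor, and Protocol 9.6.4 describes a multivariable model that names both missing factors. This stands in part: a reader should not infer that no information on risk factors would exist. But univariate screens are not the multivariable answer SAP 7.1 promises. SAP 7.1 is not silent either: it names a different model, and Protocol 9.0 gives it precedence. Nor is it proven that the two factors are barred, since SAP 7.1 says they will be included. The SAP is inconsistent with its own list and must be reconciled.

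**The primary analysis is hardly touched.** This stands. The rule is prespecified and does not raise type I error. Losses of 3.1-5.3 points of power appear only with sites spread over 40-95%, for which the documents give no basis.

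**The interaction rule might look far worse.** If all 13 factors were tested, a false interaction would appear in 1 - 0.95^13 = 48.7% of trials, and simulation with the arm coefficient read as the result gives 18.7% false rejections. The text does not support that reading: factors first become covariates by passing the screen, and the next sentence tests those covariates. It would also be wrong to call the odds ratio undefined when an interaction enters. The arm coefficient then applies at the covariate's reference value; what is missing is a named overall contrast. The SAP's Fisher test could be read as an unadjusted comparison of the primary endpoint, but it sits under the descriptive analysis and is not designated primary.

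**A full risk-factor model would be overfitted.** This stands, and it shapes the fix.

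**Conclusion.** SAP 7.1 is wrong as written. The about 10% ceiling on entry follows from randomisation and the p<0.1 threshold, whatever the effect sizes. The 50-84% chance that no factor enters rests on assumed distributions and effects. The mismatch between the named factors and the SAP 5 list is read directly from the text.

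Leaving site out of the primary model is a small matter: about 0-1 point of power and a slightly conservative test for assumed site differences of 10-20 points. The missing overall contrast would matter in about 1-4% of null trials. A reader might infer that the primary test is biased or seriously underpowered by the covariate rule. Neither the documents nor the calculations support that.

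**What to change.** **SAP 7.1.** Restore a separate multivariable logistic model of the listed factors plus arm and site, entered regardless of balance between arms. Before database lock, fix a limited set with one variable per domain, merging the overlapping substance-use measures, or specify penalised estimation. Report the model as exploratory. Name the stigma and disclosure scale for fear of disclosure and the PHQ9 for mental illness, stating that the PHQ9 records symptoms and not whether the illness is treated.

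**SAP 6.** Include site, meaning the randomisation strata, in the primary model. First reconcile the three sites of Protocol 2.2 with the four of Protocol 3.1. Take the primary odds ratio, 95% CI and p-value from the main-effects model, and report interactions as exploratory.

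**Cost.** SAP wording, one extra secondary model and a few lines of code. The site code is part of every patient identifier (Protocol 4.3.3) and both scales are already collected. Site uses 2-3 degrees of freedom and makes the odds ratio conditional on site. The real limit is on Objective 1: some 60-120 non-adherent subjects cannot support about 20 parameters, so the factor set must be cut or the estimates penalised. Treatment status for mental illness is not recorded by the PHQ9.

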¹ Pre: attitudes toward safe sex, disclosure, access to care, social support, texting ability, Kalichman sexual compulsivity; Post: satisfaction with iTAB; Pre/Post: HIV literacy, stigma and disclosure, AUDIT, DAST-10 ² includes: risk behavior, adherence assessments, intention to adhere, PHQ9, SCID substance use screen ³ Perform if HIV+ ⁴ Any time history or symptoms suggest potential HIV or STI, check with study MD for appropriate test ⁵ Subjects may have an interim visit if past window of scheduled visit, next visit should be back to regular schedule ⁶ To be performed at week 36 only ⁷ Performed only once on or after Week 48 coinciding with STI screening (Week 48, 72, or 96)											

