3.2 Secondary Objectives

1. To determine factors associated with poor adherence/lost to PrEP in study participants. Factors will include demographics, ongoing substance use, untreated mental illness, socioeconomic status, low health/HIV and system literacy, fear of disclosure and non-English language.
2. To determine the rate of HIV seroconversion in PrEP users and compare the iTAB to SoC arms for number of new infections as a proportion at 48 weeks and end of the study.
3. To measure acquisition of other sexually transmitted infections (STIs); the proportion of subjects with any new STI at any site will be compared between the iTAB to SoC arms at 48 weeks and end of the study.
4. To evaluate changes in risk behavior after initiation of PrEP (risk compensation) comparing baseline to subsequent visits for number of HIV positive/unknown status partners and any unprotected anal intercourse with an HIV positive/unknown status partner.
5. To evaluate the safety and tolerability of daily TDF/FTC given for PrEP including discontinuation for any adverse event, serious adverse events, and adverse events (grade 2 or higher).

4 Subject Disposition

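### SAP 7.1 answers the predictors-of-adherence objective with a model that admits a factor only if it happens to be unbalanced between arms, so a true predictor is left out about 90% of the time or more

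*SAP*

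**What the plan says.** SAP 7.1 restates Secondary Objective 1 and gives two sentences of method: "This objective will be assessed along with the primary objective analysis", then "The final primary multivariable model will be able to answer this question". It specifies no other model.

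That model is defined in SAP section 6 under Statistical Inference. Baseline factors enter "as covariates if they are found unbalanced between the study arms" at p<0.1 and are also univariately associated with the outcome at p<0.15; both conditions are required. A further sentence reads "Interactions between each of the covariates and study arm will also be assessed individually", and interactions with p<0.05 go into the final model.

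The candidates come from SAP section 5, introduced by "The following variables will be examined at baseline". I count 13 entries, taking any drug use and methamphetamine use separately. The objective names seven domains: demographics, ongoing substance use, and "untreated mental illness, socioeconomic status, low health/HIV and system literacy, fear of disclosure and non-English language" (SAP 3.2).

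Protocol 9.6.4 treats the same question differently. It lists the named factors as potential covariates of multivariable logistic models with no balance condition, and uses the imbalance rule only to add further confounders. It also plans analyses within each arm. Protocol 9.0 gives the SAP precedence where the two differ.

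**The concern.** The section 6 rule is a way of choosing confounders for the treatment comparison. SAP 7.1 reuses it to find predictors of adherence, which is a different task. Whether a factor predicts adherence has no bearing on whether randomisation left it unbalanced, so the imbalance condition filters predictors at random.

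At stake is the content of a stated secondary objective. Followed as written, the factors in the named model would mainly be those that happened to differ between arms. A factor's absence could then be misread as evidence that it does not matter. Separately, two of the domains that SAP 7.1 promises have no variable in the list that supplies the model.

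**Working it through.** The plan gives no figure for this point. Its main-study power figures (94% and 84%, protocol 9.4) reproduce with an exact Fisher calculation (94.0% and 84.5%) but are not used below.

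**Inputs.** 1:1 allocation with 200 per arm (protocol 9.4); imbalance tested by Wilcoxon for continuous and Fisher's exact for categorical variables (SAP 5); thresholds p<0.1, p<0.15 and, for interactions, p<0.05 (SAP 6). The bounds in steps 1, 3 and 4 need no effect size or outcome rate.

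**1. One factor, main effect.** P(enter) = P(unbalanced and associated) ≤ P(unbalanced). Take a predictor certain to pass the association test, so that only imbalance matters.
- Continuous, Wilcoxon: nominal 10%; 9.9% in 20,000 simulated trials.
- Binary, Fisher: with K carriers among 400, the number in one arm is hypergeometric (400, 200, K). Summing over outcomes with two-sided p<0.1, for K = 20 to 200: minimum 3.65% (K=20), maximum 9.98% (K=118), mean 7.7%. For K = 4 to 19 it is 0 to 8.9%.

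Such a predictor is therefore dropped about 90% of the time or more. A factor unrelated to the outcome enters about 0.10 × 0.15 = 1.5% of the time.

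**2. What the imbalance condition costs.** Illustration under assumptions of mine (adherence about 70%; 4,000 trials per setting):

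| Factor | Association test alone | Both conditions |
|---|---|---|
| Binary, prevalence 30%, OR 2 | 90–92% | 7–8% |
| Continuous, OR 2 per 2 SD | 93–95% | 9–10% |

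**3. Interaction route.** If the interaction sentence covers only covariates already admitted, it adds no factor. If it covers every listed factor and there is no true interaction, P(enter) ≤ 0.10 + 0.05 = 0.15; under independence 1 − 0.90 × 0.95 = 0.145. Simulation at outcome rates of about 22%, 50% and 78% gave 0.146, 0.147 and 0.144.

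**4. Across the list.** Ten of the 13 entries correspond to a named domain: age, race/ethnicity, education, income, language, any drug use, methamphetamine, AUDIT, DAST and HIV literacy. If all ten were certain predictors:
- main effects: on average at most 10 × 0.10 = 1.0 enters, and none enters in at least 0.9^10 = 35% of trials (42% or 57% if the factors correlate at 0.3 or 0.6);
- wide interaction reading: on average at most 10 × 0.15 = 1.5 enter, and none in about 0.855^10 = 21% (independent factors).

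**5. Named factors against the list.** SAP 7.1 promises untreated mental illness and fear of disclosure; the section 5 list has no measure of either. Relevant instruments are collected at week 0. Footnote 1 to the protocol 6.1 schedule has "Pre/Post: HIV literacy, stigma and disclosure, AUDIT, DAST-10" and footnote 2 has "risk behavior, adherence assessments, intention to adhere, PHQ9, SCID substance use screen".

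**6. Outcome.** The primary TFV-DP endpoint can count someone who stops after week 12 as adherent on the week 12 sample alone (SAP 6), and dried blood spots are not collected off drug (protocol 6.4.1). It captures loss to PrEP only in part.

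**The case against.** The best defence is that SAP 7.1 points to the whole primary objective analysis, which includes the univariate association screen. Protocol 9.6.4 also plans a descriptive comparison of adherent and non-adherent subjects within each arm. The SAP is silent on that comparison, and silence is not contradiction, so it may still stand. It does not depend on balance between arms. This much is right: a reader might infer that the trial would produce no information on predictors, and the documents do not support that. But SAP 7.1 names the multivariable model as the answer and does not commit to reporting the screen, which would in any case be unadjusted.

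A second defence is that interactions can bring factors in. That test asks whether a factor modifies the intervention effect, not whether it predicts adherence, and by chance alone it lifts entry only to about 15%. A factor with a true interaction could enter more often.

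A reader might also infer that mental illness and fear of disclosure are barred from the analysis altogether. That goes too far. SAP 7.1 says they will be included, and section 5 says which variables will be examined without excluding others. The two texts conflict and must be reconciled.

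**Conclusion.** The point holds, for this secondary objective only. The model that SAP 7.1 names cannot be relied on to find predictors of adherence: it leaves out even a certain predictor about 90% of the time or more as a main effect, or about 85% or more on the wide interaction reading with no true interaction. These are per-factor figures; they rest on 1:1 randomisation, 200 per arm and the SAP's own tests and thresholds. The binary range of 3.65% to 9.98% applies to 20 or more carriers; the ceiling of about 10% applies throughout.

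It would be wrong to infer that the iTAB versus SoC comparison is compromised. The objective is associational and secondary, so this should be corrected but does not touch the trial's main conclusion.

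**What to change.** Replace the last sentence of SAP 7.1 with a separate exploratory multivariable logistic model, both arms combined, with arm and site included, that enters the factors named in the objective regardless of balance. Report univariate and adjusted odds ratios with 95% confidence intervals for every factor.

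- Add baseline PHQ-9 and pre-specified disclosure and privacy items from the stigma survey. Label both as proxies: PHQ-9 measures depressive symptoms, not whether illness is untreated, and the survey mixes attitudes to people with HIV with items on personal privacy.
- Fit the model on the primary TFV-DP endpoint and, for loss to PrEP, on the SAP's outcome of being on PrEP at week 48. The self-report composite is optional: one missed visit leaves at most 15 − 3 = 12 of the 14 days required, so it partly reflects attendance.
- Keep the arm-specific descriptive analyses of protocol 9.6.4.

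The cost is SAP wording, a scoring rule and one extra model on two outcomes, with no new data collection. The downside is possibly few events per parameter. As an illustration, the ten listed factors plus the two proxies need 14 parameters (race/ethnicity 3, the other eleven 1 each, which assumes education and income are single terms). Adding arm (1) and site (2 or 3, since protocol 2.2 counts three sites and 3.1 adds a fourth) gives 17–18. The documents state no expected TFV-DP rate. If the smaller outcome class is assumed to be 10%, 30% or 50% of 400 (40, 120 or 200 subjects), that is 2.2–2.4, 6.7–7.1 or 11.1–11.8 per parameter. Use penalised estimation if that class turns out small, and present the results as exploratory.
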